5.3 Effectiveness Endpoints Analyses

5.3.1 Primary Effectiveness Endpoint

The primary effectiveness outcomes for this study is:

- Proportion of subjects with $\geq 20\%$ decrease in mean diurnal IOP at 12 months while maintaining the same or fewer number of medications as at baseline

The primary analyses of the primary endpoint will be based on the Effectiveness Population. The exact 95% confidence interval of the response rate will be calculated based on binomial distribution.

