3.2 Screening Inclusion Criteria

Subjects must meet the following inclusion criteria to be eligible. Unless otherwise specified, all ocular criteria refer to the study eye only.

- Male and female patients at least 45 years of age
- A diagnosis of open-angle glaucoma (POAG, PXG, or PG), with optic nerve pathology described by one or more of the following:
 - Diffuse thinning, focal narrowing, or notching of the optic disc rim, especially at the inferior or superior poles with or without disc hemorrhage;
 - Localized abnormalities of the peripapillary retinal nerve fiber layer, especially at the inferior or superior poles; or
 - Optic disc neural rim asymmetry of the two eyes consistent with loss of neural tissue
- BCVA of 20/80 or better in the study eye
- Subject has refractory glaucoma, defined as:
 - Previously failed filtering or cilioablation procedure (i.e., includes incisional glaucoma surgery, cryotherapy, and cyclodiode therapy) and with uncontrolled IOP on medical therapy

or

- IOP is uncontrolled on maximum tolerable medical therapy (e.g., a minimum of four or more classes of topical glaucoma medications, or fewer if others are not tolerated or are not effective)
- Subject has been on current glaucoma medication regimen for at least 30 days
- A medicated IOP of ≥ 20 mmHg and ≤ 35 mmHg by Goldmann applanation tonometry
- Open anterior chamber angle anatomy (e.g., no peripheral anterior synechiae or iris processes) visualized by gonioscopy with a Shaffer angle grade of \geq III in all four quadrants
- Visual field examination using Humphrey-Zeiss 24-2 SITA Std., with mean deviation (MD) of -3 dB or worse (conducted within 60 days of Screening is acceptable)
- Visual field defects consistent with glaucomatous optic nerve damage, and with at least one of the following two findings:
 - A cluster of 3 or more points in an expected location of the visual field depressed below the 5% level, at least 1 of which is depressed below the 1% level on pattern deviation (PD) plot
 - Glaucoma hemi-field test “outside normal limits”
- The subject is able to understand the requirements of the study and provide written informed consent
- Subject is willing to follow study instructions, agrees to comply with all study procedures and attend all scheduled follow-up exams for 12 months postoperatively

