5.2 Study Populations

The **Effectiveness Population** will consist of all the subjects who undergo the Hydrus implantation surgery and are not discontinued early from the study due to unrelated reasons such as death or relocation. The primary analyses on the primary and secondary effectiveness endpoints will be based on the **Effectiveness Population**. The reasons for discontinuation will be reported.

Intent to Treat. The ITT population will include all subjects undergoing Hydrus Microstent implantation surgery. For this study the ITT population is the safety population.

Per Protocol. The Per Protocol (PP) population will include all implanted subjects who meet the following criteria:

- Subject meets all protocol eligibility criteria.
- Subject completes the 12-month visit.
- Subject received secondary surgical intervention (SSI) for controlling IOP will be included and treated as non-responder
- Subjects without adverse events that lower IOP such as cyclodialysis cleft.
- Additional criteria, if any, will be established before the data review and database closure.

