6.8.1 Anticipated Adverse Events

Anticipated AEs associated with glaucoma surgical procedures that might reasonably be expected to occur in this study are listed below. These specific examples of anticipated AEs include, but are not limited to:

Intraoperative Adverse Events

- Choroidal hemorrhage or effusion
- Corneal abrasion
- Corneal edema
- Cyclodialysis cleft
- Hyphema obscuring the surgeon's view
- Inadvertent perforation of the sclera
- Iridodialysis
- Lens / capsular bag damage (crystalline or IOL)
- Microstent malposition
- Significant iris injury or trauma
- Vitreous loss
- Zonular dialysis

Postoperative adverse events include

- Angle closure
- Angle recession
- Anterior chamber cell or flare requiring either an increase in the standard postoperative steroid regimen or re-initiation of steroid use following completion of the standard postoperative steroid regimen.
- Aqueous misdirection
- Atrophy, phthisis
- Best-corrected visual acuity loss of 2 lines (10 letters) or more compared to baseline on the ETDRS chart measured before or at 1-month postoperative
- Best-corrected visual acuity loss of 2 lines (10 letters) or more compared to baseline on the ETDRS chart measured after 1-month postoperative
- Blebitis
- Choroidal detachment
- Choroidal hemorrhage or effusion (detachment with at least a partially hemorrhagic component that obstructs or causes pain, including both peripheral and "kissing" choroidal detachments) lasting 30 days or less
- Choroidal hemorrhage or effusion (detachment with at least a partially hemorrhagic component that obstructs or causes pain, including both peripheral and "kissing" choroidal detachments) lasting longer than 30 days
- Chronic anterior uveitis defined as inflammation of grade 1+ or worse persisting for more than 90 days postoperatively or that recurs less than 90 days after discontinuing standard medication regimen
- Chronic pain in the study eye onset ³ 3-months postoperative
- Corneal decompensation

- Corneal edema persisting > 30 days (mild to moderate) or severe corneal edema ≥ 1 day.
- Corneal opacification
- Descemet's membrane detachment
- Device migration (dislodgement or movement)
- Device obstruction
- Elevated mean IOP ≥ 10 mmHg than the qualifying baseline mean IOP onset before or at 1-month postoperative
- Elevated mean IOP ≥ 10 mmHg than the qualifying baseline mean IOP onset after 1-month postoperative
- Endophthalmitis

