- Flat anterior chamber with lens/cornea touch or shallow anterior chamber with peripheral iridocorneal apposition
- Hyphema ≥ 2 mm in height (layered) at any time
- Hyphema present or arising > 30 days postoperative
- Hypotony (defined as IOP < 6 mmHg) onset before 1-month postoperative
- Hypotony (defined as IOP < 6 mmHg) onset at or after 1-month postoperative
- Implant corneal touch
- Implant-iris touch associated with intraocular inflammation, pigment dispersion, or other sequelae
- Inadvertent bleb
- Increase in vertical C/D ratio of ≥ 0.3 units from screening on fundus examination
- Iris prolapse/wound incarceration
- Maculopathy including hypotonic maculopathy
- Persistent diplopia
- Pupil block
- Retinal complications (e.g., flap tears, retinal break, retinal detachment, age related macular degeneration, diabetic retinopathy, macular edema, epiretinal membrane, central serous retinopathy, or proliferative vitreoretinopathy)
- Scleral ectasia
- Surgical re-intervention in the study eye (other than paracentesis to relieve pressure within the 1 week visit)
- Toxic anterior segment syndrome (TASS)
- Vitreous haze
- Vitreous hemorrhage
- Vitritis
- Worsening of 2-points (from screening) to "severe" on the slit lamp examination findings (other than cells and flare) onset at or after 3-months postoperative not associated with a pre-existing condition
- Worsening of lens opacities (defined as a 2.0 or more score change on at least one category of the LOCS III grading system, at 2 or more consecutive visits)
- Worsening of visual field (mean deviation worsening by 3.0 dB or more, confirmed by 2 repeat measurements)
- Wound dehiscence (persistent aqueous leak or fistula formation)

For any adverse event that may be due to incorrect device positioning (i.e. vitreous hemorrhage, hyphema, hypotony), gonioscopy should be performed to assess the device position. If the position cannot be adequately evaluated by gonioscopy, ultrasound biomicroscopy (UBM) should be performed.

For slit lamp examination, gonioscopy and fundus findings for which there is no grading scale, any finding considered by the study investigator to be marked or severe, i.e., clinically significant, should be recorded as an Adverse Event.

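### The primary responder rule credits a 12-month pressure fall even when it reflects a complication the plan lists as an adverse event, and no specified effectiveness analysis removes it

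*Combined protocol and SAP*

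**What the plan says.** The primary endpoint in section 5.3.1 is the proportion of subjects with a fall of at least 20%, worded as "decrease in mean diurnal IOP at 12 months while maintaining the same or fewer number of medications as at baseline". Those two conditions, pressure and medication count, are the whole definition. The result is a response rate with an exact binomial 95% confidence interval; no performance goal is stated.

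On the population, the same section says: "The primary analyses of the primary endpoint will be based on the Effectiveness Population". Section 5.2 builds that set from operated subjects who "are not discontinued early from the study due to unrelated reasons such as death or relocation". Nothing there concerns complications that lower IOP.

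The Per Protocol criteria in section 5.2 do address them, admitting "Subjects without adverse events that lower IOP such as cyclodialysis cleft". The same list says of IOP surgery: "Subject received secondary surgical intervention (SSI) for controlling IOP will be included and treated as non-responder". Both rules appear only under Per Protocol, and sections 5.3.1 to 5.3.3 assign no analysis to that set.

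Section 6.8.1 lists "Cyclodialysis cleft" among anticipated intraoperative events. Among postoperative events it lists "Hypotony (defined as IOP < 6 mmHg) onset at or after 1-month postoperative", with a matching entry for earlier onset. No text links either event to responder status.

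**The concern.** A responder rate is read as the share of eyes that benefited. If the pressure is low at 12 months because of a cleft or persistent hypotony, the same eye appears as an adverse event in the section 5.4 tables and as a success in the primary rate. Tabulating the event does not alter that rate.

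The misclassification runs one way. A complication that lowers pressure can turn a non-responder into a responder but not the reverse. The plan describes no comparator arm in which the same effect might offset it. The plan excludes such eyes from one analysis set, but that set has no assigned effectiveness analysis, so the exclusion affects no specified result.

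**Working it through.** The plan states no sample size, expected response rate or complication rate, so there is no figure of its own to reproduce. The check asks whether a hypotonous eye meets the rule, which analysis set catches it, and how far the rate could move.

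**Inputs**
- Eligible pressure: "A medicated IOP of ≥ 20 mmHg and ≤ 35 mmHg by Goldmann applanation tonometry" (section 3.2); section 3.4 requires the same 20 to 35 mmHg range for medicated diurnal IOP at baseline.
- Percent change = (postoperative − baseline) ÷ baseline × 100 (section 5.1).
- Responder threshold: a fall of at least 20% (section 5.3.1).
- Hypotony: IOP below 6 mmHg (section 6.8.1).

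**Step 1. Does a mean diurnal IOP below 6 mmHg meet the pressure criterion?** For baseline B, the highest qualifying 12-month value is 0.8 × B. The fall at exactly 6 mmHg is (B − 6) ÷ B.

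| Baseline B (mmHg) | Highest qualifying IOP (mmHg) | Fall at 6 mmHg |
|---|---|---|
| 20 | 16 | 70.0% |
| 25 | 20 | 76.0% |
| 30 | 24 | 80.0% |
| 35 | 28 | 82.9% |

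A value below 6 mmHg could miss the criterion only if B were below 6 ÷ 0.8 = 7.5 mmHg, which eligibility rules out. Every eligible eye with a 12-month mean diurnal IOP below 6 mmHg therefore meets the pressure criterion, and is a responder unless its medications have increased. An eye with an open cleft can also qualify at a pressure above 6 mmHg, since any value up to 16 to 28 mmHg is enough.

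**Step 2. Which set catches it?**

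| Set | IOP-lowering adverse event | Effectiveness analysis assigned in 5.3 |
|---|---|---|
| Effectiveness Population | kept, no special rule | primary and secondary endpoints |
| Per Protocol | excluded | none |

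**Step 3. How far could the rate move?** Let x be the number of responders among N subjects, and k the number of those responders whose 12-month pressure reflects such a complication. Counting them as non-responders changes the rate by x/N − (x − k)/N = k/N, whatever x is. One eye is 1/60 = 1.7 points at an assumed N of 60, 3.3 points at 30, and 1.0 point at 100.

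The table is an illustration only: N, a 60% response rate and k are all assumed. Exact 95% intervals are in brackets.

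| N | As written | k | Counted as non-responders | Excluded, as in Per Protocol |
|---|---|---|---|---|
| 30 | 18/30 = 60.0% (40.6–77.3) | 1 | 17/30 = 56.7% (37.4–74.5) | 17/29 = 58.6% (38.9–76.5) |
| 30 | 18/30 = 60.0% (40.6–77.3) | 3 | 15/30 = 50.0% (31.3–68.7) | 15/27 = 55.6% (35.3–74.5) |
| 60 | 36/60 = 60.0% (46.5–72.4) | 1 | 35/60 = 58.3% (44.9–70.9) | 35/59 = 59.3% (45.7–71.9) |
| 60 | 36/60 = 60.0% (46.5–72.4) | 3 | 33/60 = 55.0% (41.6–67.9) | 33/57 = 57.9% (44.1–70.9) |
| 100 | 60/100 = 60.0% (49.7–69.7) | 1 | 59/100 = 59.0% (48.7–68.7) | 59/99 = 59.6% (49.3–69.3) |
| 100 | 60/100 = 60.0% (49.7–69.7) | 3 | 57/100 = 57.0% (46.7–66.9) | 57/97 = 58.8% (48.3–68.7) |

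Exclusion moves the rate less than non-response because it also shrinks the denominator. A Per Protocol rate, even if one were assigned, would not be the same correction.

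**The case against.** The best defence is that an inclusive primary set with a stricter Per Protocol set is a common design, that adverse events are tabulated separately, and that section 5.3.3 summarises IOP at every visit with a range, so a very low 12-month value would be visible. In the illustrations the shift from one eye lies well inside the confidence interval, and without a stated performance goal no declared decision can flip. All of this is fair, and it limits the severity. It does not change the primary rate, and the stricter set has no analysis assigned to it.

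Three stronger readings are tempting and are not supported.

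- A reader might infer that any eye with hypotony becomes a success. The endpoint uses the diurnal mean at 12 months, from three readings (section 4.0, schedule footnote). Hypotony that resolved earlier does not by itself create a responder.
- A reader might assume a prevalence of, say, 1–3% and conclude that the rate is overstated by 1–3 points. That only restates the assumption. It is also an upper bound: an eye on more medications already fails, and some affected eyes might have reached a 20% fall without the complication.
- A reader might take the Per Protocol exclusion as proof that the sponsor does not regard such falls as device effect. Section 5.2 only removes these subjects from that set, as it also removes ineligible subjects and those without a 12-month visit. Where it wants non-responder status, for IOP surgery, it says so.

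A practical objection also stands. The event characteristics recorded under section 6.2 do not include whether an event lowers IOP, so an ongoing IOP-lowering event cannot be identified consistently without a list of terms fixed in advance.

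**Conclusion.** The point holds for complications still lowering IOP at the 12-month visit. As written, the primary rate counts these eyes as successes when medications have not increased, and no specified effectiveness analysis shows the rate with them counted as failures. The direction is certain: the rate can only be raised, by at most k/N. The size cannot be derived, because the documents give neither N nor a rate of late hypotony or persistent cleft. The figure of 1.7 points per eye rests on an assumed N of 60. Severity is minor to moderate: a gap in the definition of the primary endpoint, probably affecting few eyes, that is cheap to close before the data are seen.

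**What to change.** In section 5.3.1, state that two groups stay in the denominator as non-responders:
- subjects with hypotony as the plan already defines it, judged on the 12-month diurnal IOP; the text should say whether this means the mean or any single reading, because section 6.8.1 does not;
- subjects with an IOP-lowering adverse event from a prespecified list (for example, cyclodialysis cleft) that is ongoing at 12 months.

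Reconcile this with the Per Protocol criterion in section 5.2. Otherwise the same subject is a non-responder in one analysis and absent from the other without explanation.

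If the sponsor keeps the endpoint unchanged, prespecify a sensitivity analysis of the primary rate that counts these subjects as non-responders, and report it beside the primary result.

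No new measurements are needed: the 12-month diurnal IOP is in the schedule, and section 6.6 follows adverse events to resolution or stabilisation. The cost is a short event list agreed before database closure and a response rate that may be slightly less favourable.

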5.3.2 Secondary Effectiveness Endpoint

The secondary effectiveness endpoint for this study is:

- Mean reduction in diurnal IOP at 12 months.

The change in diurnal IOP from baseline at 12 months will be calculated for each subject, and the mean change in diurnal IOP and the corresponding 95% confidence interval will be calculated.

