4.0 CLINICAL FOLLOW-UP SCHEDULE

All subjects will be scheduled to return for follow-up examinations at defined intervals through 12 months. **Table 5** shows the schedule of events and procedures at each protocol-required visit.

SCHEDULE OF VISITS

| Procedure | Screening ¹ | Baseline (30 days from Scr) | Surgery (30 days from BL) | 1D Postop (+/- 2D) | 7D Postop (+/- 2D) | 1M Postop (30+/- 7D) | 2M Postop (60+/- 10D) | 3M Postop (90+/- 14D) | 6M Postop (183+/- 14D) | 9M Postop (274+/- 30D) | 12M Postop (365+/- 45D) |
|---|------------------------|--------------------------------|------------------------------|-----------------------|-----------------------|-------------------------|--------------------------|--------------------------|---------------------------|---------------------------|----------------------------|
| Informed Consent | X | | | | | | | | | | |
| Medical History Ophthalmic and Non-Ophthalmic | X | | | | | | | | | | |
| Medication Assessment | X | X | X | X | X | X | X | X | X | X | X |
| Manifest Refraction | X | X | | X | X | X | X | X | X | X | X |
| BCVA - Snellen | X | | | | | | | | | | |
| Visual Acuity-Pinhole | | | X | | | | | | | | |
| BCVA - ETDRS | | X | | | X | X | X | X | X | X | X |
| Intraocular Pressure Goldmann Applanation Tonometry | | X | | X | X | X | X | X | X | X | X |
| Diurnal Intraocular Pressure Goldmann Applanation Tonometry | | | X ³ | | | | | | | | X ³ |
| Intraocular Pressure 2 to 6 hours after surgery | | | | X ⁴ | | | | | | | |
| Pachymetry CCT | X | | | | | X | X | X | X | X | X |
| Gonioscopy | X | | | | | X | X | X | X | X | X |
| Slit Lamp Exam | X | X | | X | X | X | X | X | X | X | X |
| Lenticular Opacity Grading | X ⁵ | | | | | X ⁵ | | | X ⁵ | | X ⁵ |
| Visual Field Humphrey 24-2 SITA Standard | X | | | | | | X | X | X | X | X |
| Fundus Exam/Disc Evaluation | X | | | | | | X | X | X | X | X |
| Optic Disc Photography | X | | | | | | | | | | X |
| Subject Questionnaire | X | | | | | | | X | | | X |
| Hydrus Implantation | | | | X ⁶ | | | | | | | |
| Adverse Event Assessment | | | | X | X | X | X | X | X | X | X |

¹ At the Screening Visit, all assessments will be performed for both eyes.

² At the Baseline Visit, both eyes may be evaluated if eligibility confirmed after all Screening procedures completed.

³ Daytime-Diurnal IOP measurements will be performed 3 times at 8:00 AM (± 1 hour), 12:00 PM (± 1 hour), and 4:00 PM (± 1 hour).

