5.0 STATISTICAL METHODS

5.1 General Data Handling

Descriptive statistics on continuous variables will include mean, standard deviation, median, and range. Confidence intervals will be included for selected endpoints. Categorical variables will be summarized using frequency counts and percentages. A confidence level of 95% will be used for the confidence intervals. Statistical testing will be two-sided with a significance level of 0.05 or one-sided with a significance level of 0.025 unless specified otherwise. Data listings of individual subject data may be provided.

The baseline values are those that are obtained at the closest visit prior to the surgery. The arithmetic difference between the baseline and the postoperative visit are defined as follows:

Change from baseline = postoperative value – baseline value

Percent change from baseline = change from baseline ÷ baseline X 100.

The Safety Population includes all subjects for whom a Hydrus microstent was implanted or implantation was attempted.

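### Section 5.3.2 gives no rule for IOP after secondary surgery for pressure control, so the mean 12-month reduction may be tilted towards the device

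*Combined protocol and SAP*

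**What the plan says.** Section 5.3.2 defines the secondary endpoint as the mean reduction in diurnal IOP at 12 months. Its analysis is one sentence: "The change in diurnal IOP from baseline at 12 months will be calculated for each subject, and the mean change in diurnal IOP" is reported with a 95% confidence interval. Section 5.1 gives the arithmetic, "Change from baseline = postoperative value" less the baseline value, with no adjustment for anything that happens in between.

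Section 5.2 sets the population: "The primary analyses on the primary and secondary effectiveness endpoints will be based on the" Effectiveness Population. That set is everyone who has the implantation surgery, provided they "are not discontinued early from the study due to unrelated reasons such as death or relocation". Further surgery for pressure control is not an unrelated reason of that kind, so such eyes are not removed.

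The analysis plan mentions SSI once, as a bullet of the Per Protocol definition: "Subject received secondary surgical intervention (SSI) for controlling IOP will be included and treated as non-responder". Another bullet limits that set to "Subjects without adverse events that lower IOP such as cyclodialysis cleft".

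On follow-up, section 4.0 says "All subjects will be scheduled to return for follow-up examinations at defined intervals through 12 months", and the 12-month visit carries the three-time diurnal measurement ("Daytime-Diurnal IOP measurements will be performed 3 times at 8:00 AM", then noon and 4 PM). The only shorter follow-up stated is in a footnote to the visit schedule, for subjects who do not receive the microstent. Section 6.8.1 lists surgical re-intervention in the study eye among the anticipated adverse events. No control arm is described.

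**The concern.** Subjects have refractory glaucoma (section 3.2), so some may need further surgery for pressure within 12 months. Section 5.3.2 keeps these eyes in the analysis set but does not say what IOP value they contribute. Two things can follow:

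- The eye is measured at 12 months. Its reading reflects the microstent plus the later operation, and the whole fall from baseline goes into a mean that will be read as the effect of the microstent. With no control arm, nothing offsets this.
- The eye has no 12-month reading. With no missing-data rule in section 5, it has no change to average, and a device failure leaves the mean.

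Both tend to make the reported reduction larger. The Per Protocol definition shows that the plan sees the issue: it counts SSI as non-response and leaves out eyes with other pressure-lowering events. That protection does not reach the main analysis of the only secondary endpoint. Responder status would not settle it in any case, because it gives no number to average.

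**Working it through.** The documents give no SSI rate, expected mean change or standard deviation, so there is no plan figure to reproduce. What can be shown is how the all-observed mean differs from one in which SSI eyes are credited with no change.

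**Inputs from the documents**
- Eligible baseline diurnal IOP: 20 to 35 mmHg (section 3.4).
- Responder threshold: a 20% fall (section 5.3.1).
- Hypotony: IOP below 6 mmHg (section 6.8.1).

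**Assumptions**
- p, the share of eyes with SSI: 5%, 10% and 20%.
- r, the fraction of SSI eyes with a 12-month reading: 0 to 1.
- m, the mean fall in the other eyes: 5 mmHg.
- F, the mean observed fall from baseline in SSI eyes: 4 to 7 mmHg. This is 0.20 × 20 = 4 and 0.20 × 35 = 7. It borrows the responder threshold only to have a scale; that threshold says nothing about falls after SSI.

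**Formulas**
- All-observed mean fall: [(1 − p)m + p·r·F] / [(1 − p) + p·r].
- Mean fall with every SSI eye at 0: (1 − p)m.
- Difference if all SSI eyes are read (r = 1): p·F.
- Difference if none are read (r = 0): m − (1 − p)m = p·m.

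**Results (mmHg)**

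| p | all read, F = 4 to 7 | none read, m = 5 |
|---|---|---|
| 5% | 0.20 to 0.35 | 0.25 |
| 10% | 0.40 to 0.70 | 0.50 |
| 20% | 0.80 to 1.40 | 1.00 |

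Check of an intermediate case, p = 10%, r = 0.5, m = 5:
- F = 4: (4.5 + 0.2)/(0.90 + 0.05) = 4.95, against 4.5, a difference of 0.45.
- F = 7: (4.5 + 0.35)/0.95 = 5.11, a difference of 0.61.

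**Limits of these figures**
- F is the whole fall from baseline, including anything the device achieved. The part due to surgery is p × (fall after SSI − fall before SSI). With p = 10%, an assumed fall of 2 mmHg before SSI and 10 mmHg after, the surgical part is 0.10 × 8 = 0.8 mmHg, while p·F is 0.10 × 10 = 1.0 mmHg.
- An SSI eye ending at 6 mmHg would have fallen 20 − 6 = 14 to 35 − 6 = 29 mmHg, or 1.4 to 2.9 mmHg in the mean at p = 10%. This is not a maximum, because section 6.8.1 anticipates IOP below 6 mmHg.
- If all SSI eyes are read and on average end above baseline, F is negative and the difference reverses.

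**The case against.** The strongest reply is that an all-observed mean is a legitimate estimand: it describes pressure at 12 months after the microstent and whatever followed. That stands, but section 5.3.2 does not say that this is what it estimates, and without a control arm the result describes the microstent plus later surgery.

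Second, the plan never says in words that readings after SSI will be used, and an SSI eye might have no 12-month reading. This also stands, and it limits the claim to a missing rule with two possible consequences. It does not remove the problem, because a missing reading takes a failure out of the mean (a difference of p·m, not zero).

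Third, assigning zero change is a convention. It can understate the device in an eye where it worked in part, and flatter it in an eye whose pressure had risen above baseline. It also deals with surgery only, while added glaucoma medication can lower the 12-month value too. All of this is fair, and is why zero change should be shown beside the observed mean and not in its place.

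Fourth, SSI is stated to be non-response only for the Per Protocol set. Changing 5.3.2 alone could give an eye zero change in the secondary analysis and a response in the primary one. This stands and widens the fix.

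Finally, re-interventions will be tabulated as adverse events under section 5.4. That helps the reader but does not correct the mean. It is also less certain than it looks: section 6.2 says that a treatment should not itself be recorded as the event, whereas section 6.8.1 lists re-intervention as one. Neither that entry nor the action codes in section 6.7 record whether the surgery was for pressure.

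**Conclusion.** The concern holds as a missing rule that tends to favour the device. Section 5.3.2 averages change over a population that keeps SSI eyes, and nothing says how IOP after SSI is treated. At an assumed 10% SSI, the all-observed mean fall exceeds the mean with SSI eyes at zero by 0.4 to 0.7 mmHg if all are read and F is 4 to 7 mmHg, and by 0.5 mmHg if none are read and m is 5 mmHg. The shares and falls are assumptions, so the true size is unknown.

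A reader might infer that the plan is certain to credit surgical pressure falls to the microstent. The documents do not support that: they schedule implanted subjects through 12 months but do not say that SSI eyes will be read then, and they give no SSI rate. Nor do they support taking p·F as the surgical contribution.

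This is a secondary endpoint with no hypothesis or success criterion in 5.3.2, so the consequence is minor to moderate. It is a cheap improvement.

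**What to change.** - In section 5.2, state that SSI for pressure control counts as non-response in the Effectiveness Population as well as the Per Protocol set, so that 5.3.1 and 5.3.2 agree.
- In section 5.3.2, report the mean change and 95% confidence interval (a) as observed, saying that this includes the effect of later surgery, and (b) with every such SSI eye set to 0 mmHg change, whether or not it has a 12-month reading.
- Report the number of SSI eyes and how many have a 12-month reading.
- Record for each re-intervention whether it was for pressure control.
- Optional sensitivity analysis: use the last scheduled postoperative IOP before SSI. This is a single reading, not a three-time diurnal mean, and may be selected for being high.
- State in the report that neither mean removes the effect of added glaucoma medication.

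The cost is a few sentences, one extra table row and one data item. The plan already needs SSI status for its Per Protocol rule, and the diurnal IOP is already scheduled. The downsides are that the reported reduction may be smaller, and that the interval for (b) treats assigned values as observed and so ignores their uncertainty. The rule should be fixed before the data are reviewed.
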